### 2.2 Outcome Variables

#### 2.2.1 Primary Outcome:

Symptomatic Hemorrhagic Transformation Rate (PH2) associated with clinical deterioration, defined as worsening of NIHSS score of 4 or more points within 30 days of initiating anticoagulant therapy.

#### 2.2.2 Secondary Outcomes:

1. Any parenchymal haemorrhage (PH1 or PH2) on follow-up MRI scan at  $7\pm2$  days post-enrolment.
2. Recurrent TIA/Ischemic Stroke within 90 days of enrolment.
3. Systemic hemorrhagic complication rate within 90 days of enrolment.

## 3.0 Study Design

The Eliquis Acute Stroke Safety Evaluation (EASSE) is an investigator initiated, prospective, open label, single arm phase IV study.

Consecutive patients with atrial fibrillation (new onset or previous history) with acute ischemic stroke or TIA will be screened from Emergency Department or stroke unit. A total of 50 male and female patients will be recruited within 24 hours of initiation of apixaban after TIA or stroke. Informed consent will be obtained from the patient or substitute decision maker, in all cases prior to enrolment. Patients will be approached by the Stroke team or stroke unit attending physicians participating in the trial.

## 4.0 Enrolment Criteria

### 4.1 Inclusion Criteria

1. Male or female patients
2. Must be  $\geq 18$  years of age.
3. Diagnosis of minor ischemic stroke, or Transient Ischemic Attack (TIA, defined as acute focal neurological deficits, with complete resolution of symptoms within 24 h of onset). In cases where onset time cannot be established, it will be considered to be the time when patient was last known to be well.
4. CT scan or MRI, with findings consistent with an ischemic etiology of symptoms.
5. Atrial Fibrillation (AF, paroxysmal or persistent), confirmed with ECG/Holter monitor, or by history (clinical documentation of previous AF must be provided).
6. Patients prescribed apixaban by their treating physician following their stroke/TIA.
7. Ability to obtain consent from patient or legally authorized representative.

**Note:** The decision to treat with apixaban and the timing of the first dose will be determined by the attending physician, independent of the registry. Consent to participate in the registry will be obtained only after the treating physician has made the decision to initiate apixaban therapy within 14 days of stroke/TIA.

### 4.2 Exclusion Criteria

1. Acute or chronic renal failure, defined as eGFR  $<30$  ml/min (Cockcroft Gault formula).
2. Known hypersensitivity to apixaban.
3. Prior treatment with apixaban or any other novel oral anticoagulant (including all Factor Xa antagonists). Treatment with warfarin prior to the stroke/TIA is acceptable, but enrolment cannot begin until the INR is  $\leq 2.0$ .
4. Any significant ongoing systemic bleeding risk, i.e. active GI/GU bleeding or recent major surgery.
5. Any condition that, in the judgment of the investigator could impose hazards to the patient if study therapy is initiated or affect the participation of the patient in the study.
6. Recent past history or clinical presentation of ICH, subarachnoid haemorrhage (SAH), arterio-venous (AV) malformation, aneurysm, or cerebral neoplasm. At the discretion of each Investigator.
7. Hereditary or acquired haemorrhagic diathesis.
8. Stroke mimics (such as seizures, migraine etc.)
9. Contraindications to MRI, including metallic implants.

## 5.0 Treatment

Patients in whom apixaban is initiated within 14 days of TIA/stroke symptom onset will be included in the registry. The timing of initiation of therapy within that 14 day window will be determined by the treating physician. Patients fulfilling at least two of the following characteristics, will have received a reduced dose of ELIQUIS 2.5 mg twice daily: age  $\geq 80$  years, body weight  $\leq 60$  kg, or serum creatinine  $\geq 133$   $\mu\text{mol/L}$  (1.5 mg/dL). All other patients will have received a 5 mg dose to be taken orally twice daily.

## 6.0 Study Procedures and Evaluations

### 6.1 Screening/Baseline

The screening/baseline visit will be conducted within 24 hours of the initiation of apixaban in the patient as decided by their treating physician. All stroke patients will initially be screened with a non-contrast CT scan of the brain (standard of care).

Standard clinical assessments and data will be collected. This will include baseline National Institutes of Health Stroke Scale (NIHSS), Premorbid Modified Rankin Scale (mRS), Montreal Cognitive Score (MoCA) and vital signs, which will be recorded in a case report form. Past medical history and medications, baseline complete blood count, coagulation profile and renal function tests will also be recorded.

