## 9.0 Central Imaging Adjudication and Analysis

Dicom CT and MRI data will be transferred to the Stroke Imaging Laboratory at the University of Alberta for post-processing and analysis. All image assessments will be performed using software developed specifically for CT brain image analysis (Quantomo software package, Cybertrial Inc, Calgary, AB). The extent of any objective acute and chronic ischemic changes on all CT scans will be assessed using Alberta Stroke Program Early CT Scores (ASPECTS). The extent of subacute ischemic changes will also be assessed using the day 1 MRI (Diffusion-Weighted Imaging sequences). Infarct volumes will be measured objectively using planimetric techniques. The extent of periventricular leukoarosis will also be measured using planimetric techniques and an intensity threshold algorithm included in the Quantomo software package.

[figure not shown]
All cases of hemorrhagic transformation seen on post-dabigatran treatment scans will be graded using the ECASS (European Cooperative Acute Stroke Study) hemorrhage classification scheme:

1. PH2 - parenchymal hemorrhage as a blood clot in more than 30% of the infarcted area with substantial space-occupying effect.
2. PH1 - parenchymal hemorrhage as blood clots in 30% or less of the infarcted area with some slight space-occupying effect.
3. HT2 - hemorrhagic transformation 2 - confluent petechiae within the infarcted area but no space-occupying effect.
4. HT1 - hemorrhagic transformation 1 – small petechiae along the margins of the infarct.
5. R - remote ICH, i.e. not topographically related to the infarct (most often in the contralateral hemisphere).

A symptomatic ICH (primary endpoint) will be defined as PH2, associated with an NIHSS deterioration of  $\geq 4$  points. The primary endpoint will be assessed using the day 7 MRI scan and any additional scans performed within 30 days of apixaban initiation.

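### The primary window opens at the first apixaban dose, but enrolment and baseline NIHSS may come up to 24 hours later, so a bleed in that gap can go uncounted

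*Protocol*

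**What the plan says.** **Clock for the primary endpoint.** Protocol 2.2.1 requires PH2 with clinical deterioration, "defined as worsening of NIHSS score of 4 or more points within 30 days of initiating anticoagulant therapy". Section 9.0 uses the same origin: the endpoint is read from the day 7 MRI and "any additional scans performed within 30 days of apixaban initiation".

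**Timing of enrolment and baseline.** Section 3.0: "A total of 50 male and female patients will be recruited within 24 hours of initiation of apixaban after TIA or stroke". Section 6.1: "The screening/baseline visit will be conducted within 24 hours of the initiation of apixaban in the patient as decided by their treating physician". The baseline NIHSS is taken at that visit.

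**Order of dose and consent.** The note under 4.1 leaves the first dose to the attending physician and places consent after the decision to treat. It does not require consent to precede the dose. Section 5.0 describes the dose as something patients have already received. In 4.2, by contrast, exclusion 3 bars earlier apixaban, and exclusion 5 speaks of hazards should therapy be started. Both read as if screening comes first.

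**Other clocks.** Secondary outcomes 2 and 3 run from enrolment, for example "Systemic hemorrhagic complication rate within 90 days of enrolment". Section 6.2.2 collects supplemental imaging for 30 days from enrolment, whereas 9.0 counts from the first dose.

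**The concern.** A patient can be on apixaban, and inside the primary endpoint window, before eligibility is judged and before the registry records an NIHSS. Suppose the first dose is at hour 0, a PH2 with a 5-point worsening occurs at hour 12, and the screening visit is at hour 20. The protocol has no rule that makes this an outcome. The investigator may exclude the patient for intracranial haemorrhage (exclusion 6) or on general judgment (exclusion 5). A systemic bleed could lead to exclusion under criterion 4. If the patient is enrolled, the baseline NIHSS already contains the 5 points, and no further 4-point worsening need appear.

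Both routes remove events and neither adds any. Section 2.1 says safety will be established by showing low haemorrhage rates, so the error favours the study's own conclusion. The rates are also meant to inform a later randomised trial (1.1). No analysis can recover a patient who was never enrolled or a pre-dose score that was never captured.

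**Working it through.** **1. The clocks side by side**

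| Item | Section | Starts at |
|---|---|---|
| Primary endpoint, 30 days | 2.2.1, 9.0 | First dose |
| Recruitment | 3.0 | Within 24 h of first dose, order not stated |
| Baseline NIHSS | 6.1 | Within 24 h of first dose, order not stated |
| First MRI | 6.2.1 | Within 24 h of recruitment, so up to 24 + 24 = 48 h after the dose |
| Supplemental imaging, 30 days | 6.2.2 | Enrolment |
| Secondary outcomes 2 and 3, 90 days | 2.2.2 | Enrolment |

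If enrolment follows the dose, the imaging collection rule omits the gap. If it precedes the dose, the rule stops up to 24 h before the endpoint window closes.

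**2. Inputs for the size.** From section 7.0: n = 50 (a convenience sample) and a 2% reference rate. The protocol states no power or derived sample size, so there is no figure of its own to reproduce. The share f of 30-day events that fall between first dose and baseline is not in the documents and is varied below as an assumption.

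**3. Even hazard, every patient enrolled a full 24 h after dosing**

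f = 24 h / (30 × 24 h) = 1/30 = 3.3%.

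- Events absorbed into baseline: observed rate = p(1 − f) = 0.02 × 29/30 = 1.93%.
- Events screened out and the patient replaced: p(1 − f)/(1 − pf) = 0.01933/0.99933 = 1.935%, practically the same.
- Expected events lost: 50 × 0.02 × 1/30 = 0.03.
- Chance of seeing no event: 0.98^50 = 36.4% without loss, and (1 − 0.01933)^50 = 37.7% with it.

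**4. Range if risk is concentrated after dosing (assumed values of f, absorbed case)**

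| f | Observed rate if true rate is 2% | Expected events lost in 50 | P(no event) |
|---|---|---|---|
| 0 | 2.00% | 0 | 36.4% |
| 1/30 | 1.93% | 0.03 | 37.7% |
| 0.10 | 1.80% | 0.10 | 40.3% |
| 0.25 | 1.50% | 0.25 | 47.0% |
| 0.50 | 1.00% | 0.50 | 60.5% |

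The screened-out case differs by less than 0.4 percentage points in P(no event).

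**5. What one lost event would do.** The result moves from 1/50 (2.0%, exact 95% CI 0.05% to 10.6%) to 0/50 (0%, 95% CI 0% to 7.1%). This is the granularity of 50 patients and would apply to any missed event. It does not estimate the bias.

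**The case against.** The strongest reply is that this is an ambiguity and not a demonstrated bias.

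- The 24-hour limit is two-sided. A visit before the dose satisfies it, and exclusions 3 and 5 suggest that order. This stands: events can be lost, but the text does not show that they are.
- Exclusion 6 is left to the investigator's discretion, so removal is not automatic. This stands.
- The protocol does not name the reference NIHSS for the 4-point worsening. Using the baseline score is an inference, although it is the only scheduled score before day 7. Section 9.0 also places a scan between dose and enrolment inside the endpoint window. Even so, a bleed visible on the scan still needs the NIHSS worsening to count.
- An enrolled patient's early PH2 would probably still appear on the day 7 MRI, so the major secondary endpoint is largely protected for enrolled patients. This stands.
- With the dose allowed up to day 14 and a Day 90 visit window of ±30 days, shifting the 90-day windows by a day matters little numerically. This is fair. The case for shifting them is consistency, and that gap events are counted.

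A reader might infer that section 1.1 shows the risk to be concentrated in this gap. It does not: that section speaks of risk soon after the stroke, and the gap is measured from the first dose. A reader might also infer that exclusion 3 flatly bars anyone already dosed. Its next sentence refers to warfarin before the index event, and inclusion 6 requires apixaban prescribed after it, so exclusion 3 most naturally means treatment before the index event. The wording needs clarifying, but it is not a firm contradiction.

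**Conclusion.** The point holds as a possible, one-directional loss of events. The primary window opens at the first dose, the protocol permits eligibility and baseline NIHSS to be settled up to 24 hours later, and nothing says that a bleed in between counts. Any bleed lost this way lowers the reported haemorrhage rate.

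The documents do not give the size. Under an even hazard with the longest permitted gap in every patient, it is small: 2.0% becomes about 1.93%, with 0.03 expected events lost in 50. Any pre-dose or earlier enrolment reduces it further. A claim that, say, one in five primary events would be lost needs risk concentrated just after dosing, and nothing in the documents supports such a figure. The correction is still worth making because the error runs toward the study's safety claim, cannot be repaired at analysis and is cheap to remove.

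**What to change.** Amend the protocol as follows.

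1. Reconcile 3.0, 4.1, 4.2, 5.0 and 6.1 on whether enrolment may follow the first dose.
2. Define registry eligibility status and the reference NIHSS as of the last assessment before the first dose, using the charted score when consent comes later. A bleed after the dose then counts as an outcome. This concerns registry status only and leaves the investigator's clinical judgment untouched.
3. Word exclusion 3 as treatment before the index event.
4. Start the windows for secondary outcomes 2 and 3, and the supplemental-imaging window in 6.2.2, at the first dose, to agree with 2.2.1 and 9.0.
5. Record the date and time of the first dose and of the reference NIHSS in the CRF.
6. From the log of consecutively screened patients, report how many bled, deteriorated or died between first dose and consent. Make this an aggregate count where ethics approval allows, since 3.0 requires consent before enrolment and patient-level data on non-consenting patients would not be available.

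The cost is a wording amendment, a few CRF fields and possibly an ethics submission for the count. Some reference scores will come from the chart, and the reported rate may be slightly less favourable.

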### 6.2 Imaging Procedures

#### 6.2.1 MRI Study 1: Performed within 24 hours of recruitment

All MRI sequences will be completed in approximately 20 minutes. The MRI protocol will consist of a T1-weighted sagittal localizer, time of flight MRA and diffusion-weighted (DWI) and perfusion-weighted images (PWI; in patients without any contraindications to gadolinium contrast). Single shot Echoplanar (EPI) DWI images obtained using diffusion gradient strengths (b values) between 0 s/mm^2, equivalent to a T2-weighted image, and 1000 s/mm^2, applied in 3 orthogonal planes, will be obtained. The DWI acquisition parameters will be: repetition time (TR) of 3 s, spin echo time (TE) of 86 ms, 8 averages, 128x128 matrix base resolution zero filled to 256x256, 22 cm field-of-view, and 1396 Hz/pixel acquisition bandwidth. The entire brain will be imaged using 19 contiguous axial slices each 5 mm in thickness, with a 1.5 mm inter-slice gap.

#### 6.2.2 MRI Study 2: Imaging studies repeated at day 7 ( $\pm 2$ days)

All imaging sequences including susceptibility weighted imaging will be repeated at day 7 ( $\pm 2$  days) after enrolment, in order to assess for early asymptomatic hemorrhagic transformation.

In the event of any clinical deterioration, a repeat CT scan will be performed immediately. We hypothesize micro-hemorrhages may predict symptomatic bleeding. In addition, any supplemental brain imaging completed within the first 30 days after enrolment will be collected.

### 6.3 Clinical Follow-up Assessments

All patients will be followed for 90 days. This is the standard post-stroke assessment period (the majority of neurological and functional recovery occurs within this time frame). Patients will be assessed clinically at follow-up visits performed on Day 7 ( $\pm 2$  days), and Day 90 ( $\pm 30$  days) by a study team member (i.e. co-investigator, study coordinator). At each visit, vital signs will be noted, a comprehensive neurologic examination will be performed and mRS, NIHSS and MoCA

assessments will be conducted with the patient. Patients will be interviewed in detail to identify and ascertain any recurrent vascular event suggestive of a stroke or TIA. Work-up to determine the underlying etiology of stroke will be reviewed and any change in management plan will be recorded.

## 7.0 Statistics

The primary outcome will be tested with a single sample t-test. The null hypothesis is that the frequency of symptomatic hemorrhagic transformation is <2%. A convenience sample of 50 patients is planned initially. This will provide initial safety and feasibility data that can be used to plan future definitive studies as required. The primary efficacy analysis will be on an intention-to-treat basis.

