## 2.0 Study Objectives

### 2.1 Overall Aim and Hypothesis

The primary aim of the Eliquis Acute Stroke Safety Evaluation registry is to demonstrate the safety of early anticoagulation with apixaban following cardioembolic stroke and TIA. Safety will be established by demonstrating low rates of hemorrhage in this setting. The secondary study objective is to document the rate of recurrent cerebrovascular ischemic events. It is fully recognized that this uncontrolled registry study is not properly designed and underpowered to demonstrate a reduction in cerebrovascular ischemic events.

We hypothesize that early initiation of apixaban within the first 14 days of stroke or TIA is not associated with increased symptomatic intracranial haemorrhage.

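### The rare yes/no primary outcome is to be tested with a one-sample t-test, which is undefined at zero events and understates an excess once there are three or more

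*Protocol*

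**What the plan says.** Section 7.0 (Statistics) names the primary test: "The primary outcome will be tested with a single sample t-test". It sets the reference in the next sentence, "The null hypothesis is that the frequency of symptomatic hemorrhagic transformation is <2" percent, and gives the size: "A convenience sample of 50 patients is planned initially". It states no significance level, sidedness, alternative rate or power, and no exact test or confidence interval is named anywhere in the protocol.

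The outcome being tested is defined in section 2.2.1 as "Symptomatic Hemorrhagic Transformation Rate (PH2) associated with clinical deterioration, defined as worsening of NIHSS score of 4 or more points within 30 days" of starting anticoagulation. The Protocol Summary and section 9.0 define it in the same terms. Each patient either has the event or does not, and the study reports the proportion who do. The design is a single arm (section 3.0), so the only comparison is with the fixed 2%.

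**The concern.** A one-sample t-test compares a mean with a constant and takes its standard error from the spread of the sample. For a rare binary outcome in 50 patients this goes wrong in two ways.

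- With no events, every observation is 0, the SD is 0, and the t statistic is a division by zero. Section 2.1 says "Safety will be established by demonstrating low rates of hemorrhage in this setting", so the result the study hopes for is one in which its named primary analysis gives no answer.
- With several events, the estimated standard error grows with each event and is no longer tied to the variance implied by the 2% null. The test is therefore weakest where an excess of symptomatic bleeding is appearing.

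Section 1.1 says the results will be used to judge whether a larger randomized trial of early versus delayed apixaban is safe and feasible. Under the planned test, a bleeding rate four times the reference could be passed on as not significantly above 2%.

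**Working it through.** **Inputs.** n = 50, reference rate p0 = 0.02 and the one-sample t-test are from section 7.0. The binary outcome is from section 2.2.1. The protocol has no power calculation to reproduce, because 50 is a convenience sample.

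**Assumptions.** The protocol states neither the level nor the sidedness, so one-sided 5% and two-sided 5% are both shown. It gives no expected event rate, so a range is used.

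**Step 1: zero events.** The SD is 0, so t = (0 − 0.02)/0 and no p-value exists. The chance of 0/50 is (1 − p)^50:

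- p = 0.5%: 0.995^50 = 78%
- p = 1%: 0.99^50 = 61%
- p = 2%: 0.98^50 = 36%
- p = 5%: 0.95^50 = 7.7%

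**Step 2: x events.** Mean = x/50; SD = √[x(50 − x)/(50 × 49)]; t = (x/50 − 0.02)/(SD/√50) on 49 df. The exact comparison is P(X ≥ x) for X ~ Binomial(50, 0.02).

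Example, x = 4: SD = √(4 × 46/2450) = 0.2741; SE = 0.2741/√50 = 0.0388; t = 0.06/0.0388 = 1.548. The standard error under the 2% null is √(0.02 × 0.98/50) = 0.0198, about half the one the t-test uses.

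| Events | Rate | t | t-test p, one-sided | t-test p, two-sided | Exact p, upper tail |
|---|---|---|---|---|---|
| 0 | 0% | undefined | none | none | 1.00 |
| 1 | 2% | 0 | 0.500 | 1.000 | 0.636 |
| 2 | 4% | 0.714 | 0.239 | 0.478 | 0.264 |
| 3 | 6% | 1.179 | 0.122 | 0.244 | 0.078 |
| 4 | 8% | 1.548 | 0.064 | 0.128 | 0.018 |
| 5 | 10% | 1.867 | 0.034 | 0.068 | 0.003 |
| 6 | 12% | 2.154 | 0.018 | 0.036 | 0.0005 |

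The two-sided exact p-values at 4 and 5 events are also 0.018 and 0.003, so the gap does not come from mixing one- and two-sided tests.

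**Step 3: rejection rule, true size and power.** All three follow from binomial tail probabilities at the smallest count that rejects.

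| Test | Events needed | Size at 2% | Power at 8% | Power at 10% |
|---|---|---|---|---|
| t-test, one-sided 5% | 5 | 0.3% | 37% | 57% |
| t-test, two-sided 5% | 6 | 0.05% | 21% | 38% |
| Exact binomial, either convention | 4 | 1.8% | 57% | 75% |

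**The case against.** The best defence is that the choice of test seldom changes a decision. At one-sided 5% the two tests disagree only at 4 events; at two-sided 5% they disagree at 4 and 5. With 1 or 2 events the one-sided t-test p-value is slightly smaller than the exact one, and at a true 2% rate 0 to 2 events occur 92% of the time. With 0/50 nothing could point to an excess, so failure to reject is the only sensible reading whether or not the statistic exists. No stopping or go/no-go rule hangs on the p-value, and the study is a convenience-sample registry meant to give initial data.

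Part of this stands. The understatement begins at 3 events, not at the first. The 5% level is an assumption, and 2% is the null boundary, not a forecast. At 0/50 the practical loss is an interval with an upper limit more than a decision.

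It does not rescue the test. The counts where the tests disagree are 8% and 10% observed rates, four to five times the reference, which are the results a safety study most needs to read correctly. A primary analysis that may have no value should not be the one named in advance. Nor is this a detail left to a statistical analysis plan: the protocol names the test, so such a plan would have to contradict it.

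**Conclusion.** The concern holds. The protocol itself fixes an unsuitable primary test.

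- It cannot be computed at 0/50, a result with probability 36% if the true rate is 2% and 61% if it is 1%.
- From 3 events up it understates the evidence of excess bleeding: at 4/50 the one-sided p is 0.064 where the exact value is 0.018.
- Against a true 8% rate it lowers power from 57% to 37% (one-sided) or 21% (two-sided).

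The p-values rest only on n = 50 and the 2% reference. The rejection counts, size and power also assume a 5% level, and the conclusion is the same under either sidedness.

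**What to change.** In section 7.0, replace the t-test with an exact binomial analysis: report the event count and the proportion with its Clopper-Pearson 95% interval and, if a test against 2% is kept, use an exact one-sample binomial test with its level and sidedness stated. The interval is informative at every count: 0/50 gives 0 to 7.1%, 1/50 gives 0.05% to 10.6%, and 4/50 gives 2.2% to 19.2%. The secondary outcomes are also proportions, and the same method could be used for them for consistency; this is optional, since section 7.0 names no test for them.

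The cost is one sentence, with no change to sample size, visits or data collection and no statistical drawback. The change does not make a non-significant result evidence of safety. With the null placed below 2%, that reading has to rest on the upper confidence limit, which is 7.1% even with no events.

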**Overall Study Aims:**

1. Demonstrate the safety of early anticoagulation with apixaban following cardioembolic stroke and TIA.
2. Document the rate of recurrent cerebrovascular ischemic events.

**Primary Outcome:** The primary endpoint is the rate of symptomatic hemorrhagic transformation (PH2) associated with clinical deterioration, defined as worsening of NIHSS score of 4 or more points within 30 days of initiating anticoagulant therapy.

**Secondary Outcome:** The major secondary endpoint is the rate of any parenchymal haemorrhage (PH1 or PH2) seen on follow-up MRI scans at  $7\pm2$  days post-enrolment. Other secondary endpoints include recurrent TIA/Ischemic Stroke within 90 days of enrolment, and systemic hemorrhagic complication rate within 90 days of enrolment

**Population:** 50 participants will be enrolled. Participants are males and females,  $\geq 18$  years of age, with TIA or ischemic stroke and a known history of or demonstrated atrial fibrillation (paroxysmal or persistent), who can be treated with apixaban following stroke.

**Phase:** IV

**Protocol Therapy:** Patients will be treated with apixaban within 14 days of symptom onset. Patients fulfilling at least two (2) of the following characteristics, will have received a reduced dose of ELIQUIS 2.5 mg twice daily: age  $\geq 80$  years, body weight  $\leq 60$  kg, or serum creatinine  $\geq 133$   $\mu\text{mol/L}$  (1.5 mg/dL). All other patients will have received 5 mg dose taken orally twice daily.

**Study Duration:** It is estimated that recruitment will take place over 2 years in the three participating centres. Enrolment is anticipated to commence by the beginning of 2017.

**Subject Participation Duration:** All patients will be assessed clinically at Day 7 and Day 90.

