Currently, the Alliance has no data related to early use of apixaban after TIA or ischemic stroke. In ARISTOTLE, patients were not eligible for enrolment/randomization within 7 days of ischemic stroke or TIA. The contraindications section of the product monograph states apixaban should not be used in patients with 'Lesions or conditions at increased risk of clinically significant bleeding, e.g., recent cerebral infarction (ischemic or hemorrhagic)'. This is therefore an area of clinical equipoise. As with warfarin (with/without heparin bridging), stroke specialists will make individual treatment decisions, based primarily on the extent of infarction visible on CT brain scan.

Although a randomized study of delayed versus early anticoagulation with apixaban will ideally answer this question, at the moment, there is no feasibility or safety data. There is also insufficient data in the present literature to indicate what the true event rates for both symptomatic hemorrhagic transformation and recurrent cerebral ischemia are. These data can be obtained by prospectively collecting clinical and imaging data from patients who are treated, as per standard clinical practice in most Canadian stroke centres, within this 7-day period of clinical

uncertainty. The results of this registry will be used to assess the safety and feasibility of a larger randomized controlled trial of early versus delayed apixaban use after stroke/TIA.

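### The primary null hypothesis is the safe state the study sets out to demonstrate, and 50 patients cannot show a rate below 2%

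*Protocol*

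**What the plan says.** The first study aim in the protocol summary is: "Demonstrate the safety of early anticoagulation with apixaban following cardioembolic stroke and TIA". Section 2.1 repeats this as the primary aim and says how it will be met: "Safety will be established by demonstrating low rates of hemorrhage in this setting". Its formal hypothesis is that starting apixaban within 14 days "is not associated with increased symptomatic intracranial haemorrhage".

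Section 7.0 gives the analysis: "The primary outcome will be tested with a single sample t-test". It continues: "The null hypothesis is that the frequency of symptomatic hemorrhagic transformation is <2" per cent. On size it says: "A convenience sample of 50 patients is planned initially", and that this will give "initial safety and feasibility data that can be used to plan future definitive studies as required". It states no alpha, sidedness, power or alternative rate.

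Section 1.1 gives the reason for collecting the data: there is "insufficient data in the present literature to indicate what the true event rates for both symptomatic hemorrhagic transformation and recurrent cerebral ischemia are". It adds that the results will inform whether a larger randomised trial of early versus delayed apixaban is safe and feasible.

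**The concern.** A test can give evidence against its null, not for it. Here the null is the reassuring state, a rate below 2%. Rejecting it would indicate a rate of 2% or more. Not rejecting it would be the best result available, yet in a small sample with a rare event non-rejection is likely even when the true rate is well above 2%. The test therefore cannot deliver the aim of demonstrating low rates, whatever the data show.

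The risk is that a non-significant result is reported as safety demonstrated and carried into the decision on a randomised trial. Section 1.1 itself notes that the product monograph's contraindications cover recent cerebral infarction, so that reading would matter.

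**Working it through.** **Inputs.** From section 7.0: n = 50, reference rate 2%, one-sample t-test. Assumed, because the protocol does not give them: alpha of 5% (one-sided, with two-sided as a variant) and true rates of 1% to 8%. The 50 is not derived from any stated inputs, so there is no sample-size figure to reproduce.

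**1. The test as written.** With x events, the observed rate is p = x/50, the standard error is √[p(1 − p)/49], and t = (p − 0.02)/SE on 49 degrees of freedom.

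| Events | Observed rate | t | Upper one-sided p |
|---|---|---|---|
| 0 | 0% | undefined (SD = 0) | – |
| 1 | 2% | 0 | 0.500 |
| 2 | 4% | 0.71 | 0.239 |
| 3 | 6% | 1.18 | 0.122 |
| 4 | 8% | 1.55 | 0.064 |
| 5 | 10% | 1.87 | 0.034 |

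At one-sided 5%, rejection needs 5 or more events. At two-sided 5% it needs 6 or more (5 events: p = 0.068; 6 events: t = 2.15, p = 0.036). No outcome gives a negative t, so no result of this test points below 2%. The undefined case, 0 events, has probability 0.98^50 = 36% at a true rate of 2% and 0.99^50 = 61% at 1%.

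**2. How often the favourable result occurs when the rate is not low.** This is the binomial probability of too few events to reject, with 0 events counted as non-rejection.

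| Test | Rejects at | True rate 4% | True rate 5% | True rate 8% |
|---|---|---|---|---|
| t-test, one-sided 5% | 5 or more | 95% | 90% | 63% |
| t-test, two-sided 5% | 6 or more | 99% | 96% | 79% |
| Exact binomial, one-sided 5% | 4 or more | 86% | 76% | 43% |

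The exact cut-off of 4 follows from P(X ≥ 3) = 0.078 and P(X ≥ 4) = 0.018 at a rate of 2%. Even with the correct test, a true rate of 5%, which is 2.5 times the benchmark, goes unrejected about three times in four.

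**3. The hypotheses reversed (null: rate ≥ 2%).** The best possible result is 0/50. Its exact one-sided p-value is 0.98^50 = 0.364, which fails even at one-sided 10%. No result in 50 patients can reject. The number of event-free patients needed is ln(alpha)/ln(0.98), rounded up: 149 at one-sided 5% and 183 at one-sided 2.5%.

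**4. What 50 patients can exclude.** Clopper–Pearson 95% upper limits:

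- 0/50: 1 − 0.05^(1/50) = 5.8% one-sided; 1 − 0.025^(1/50) = 7.1% two-sided.
- 1/50: 9.1% one-sided; 10.6% two-sided.

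The two-sided limit at 0/50 is 7.1/2 = 3.6 times the 2% benchmark; the one-sided limit is 5.8/2 = 2.9 times.

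**The case against.** The strongest reply is that the null suits the hypothesis in section 2.1. Testing whether the rate is too high is a harm screen, a recognised use of a small single-arm cohort, and it fits a hypothesis of no increase. That reading is fair, but it does not rescue the aim: section 2.1 also says safety will be established by demonstrating low rates, and a harm screen that fails to fire does not do that. With 50 patients the screen is also weak.

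Second, the protocol never promises to show a rate below 2%. The figure appears only in the null, and the aim names no number. This is correct, and it makes the p = 0.36 calculation supporting evidence rather than the main point. The direction problem holds for any threshold, and 2% is the only benchmark the document offers.

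Third, the sample is openly a convenience sample for initial data, with no power claimed. That explains the size. It explains neither the direction of the null nor the word demonstrate, and the caveat in section 2.1 about being underpowered covers ischaemic events only.

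Fourth, alpha and sidedness may sit in a statistical analysis plan that is not at hand. Their absence is not counted here; they enter only as labelled assumptions. The null itself is stated in the protocol, and an analysis plan that follows it would inherit the fault.

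Finally, apixaban and its timing are chosen by the treating physician independently of the study, so no patient's treatment depends on this test. The harm is confined to interpretation, but this is the primary analysis of the primary safety endpoint.

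**Conclusion.** The concern holds. The primary null in section 7.0 is the state that the summary and section 2.1 say will be demonstrated, so the stated primary test cannot support the stated primary aim. This follows from the text alone and needs no assumption.

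The size depends on an assumed alpha. At one-sided 5% the planned test would return the favourable non-rejection 95%, 90% and 63% of the time at true rates of 4%, 5% and 8%. The statement that 50 patients cannot exclude 2% is robust to that choice, since 0/50 gives p = 0.36 at best. The t-test on a yes/no outcome adds a second fault: the best safety result cannot be computed as planned. Because the protocol says the true rates are unknown, estimation is the analysis that fits its purpose.

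**What to change.** - **Section 7.0.** Replace the t-test and its null with estimation as the primary analysis: the observed rate of symptomatic haemorrhagic transformation with a Clopper–Pearson two-sided 95% confidence interval. State the precision: 0/50 would exclude rates above 7.1%, 1/50 rates above 10.6%, and no result in 50 patients can exclude 2%.
- **Summary and section 2.1.** Change the aim from demonstrating safety to estimating the rate of symptomatic haemorrhagic transformation, and bring the sentence on how safety will be established into line.
- **If a test is kept.** Use an exact binomial test whose null is a rate at or above a limit justified in advance, with alpha and sidedness stated. The limit must not be chosen to fit the sample size. A harm screen could be kept instead, with an exact test, but only if the aim is reworded and the text says that non-rejection is not evidence of safety.

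The cost is rewording in three places and a less favourable stated conclusion. Sample size, eligibility and data collection do not change.
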